11 STUDY MEDICATION LABELING

11.1 PRIMARY PACKAGING

11.2 SECONDARY PACKAGING

EPREX®/ERYPO® UI/ ml

ERITROPOYETINA HUMANA RECOMBINANTE

Solución Inyectable I.V.-S.C.

Jeringa conteniendo Eritropoyetina Humana Recombinante 1.000 UI/0,5 ml. Excipientes autorizados c.s.p. Industria Holandesa.

Mantener fuera del alcance de los niños.

Sólo Uso Ensayos Clínicos. Prohibida su venta.

CONSERVAR ENTRE 2 Y 8°C. NO CONGELAR

Investigador: _____

N° de Paciente: _____

Janssen-Cilag, [name] –

[name]

Lote: Vencimiento:

HEMAX®PFS UI/ ml
ERITROPOYETINA HUMANA RECOMBINANTE
 Solución Inyectable I.V.-S.C.
 Jeringa conteniendo Eritropoyetina Humana
Recombinante 2.000 UI/0,5 ml. Excipientes
 autorizados c.s.p. Industria Argentina.
 Mantener fuera del alcance de los niños.
 Sólo Uso Ensayos Clínicos. Prohibida su venta.
CONSERVAR ENTRE 2 Y 8°C. NO CONGELAR
 Investigador: _____
 N° de Paciente: _____
 BIOSIDUS SA, [name]
 Sólo Uso Ensayos Clínicos. Prohibida su venta.
 Lote: Vencimiento:

11.3 CONCOMITANT MEDICATIONS/ TREATMENT OF ANEMIA

Transfusions: Patients will be transfused according to the clinical judgment of the investigator, based on the patient's symptoms and not on a cutoff value of hemoglobin. The transfused patients will be withdrawn from the study for having reached a study endpoint.

Iron intake: All patients will receive concomitant treatment with iron orally to maintain the levels of transferrin saturation >20% according to the indications of the treating physicians. The intravenous iron is also permitted, according to the criterion of the treating physicians.

12 STUDY DEVELOPMENT

12.1 STUDY PROCEDURES

This study will include a screening or baseline visit (a week before randomization), a randomization visit (week 0), a treatment titration phase (week 0 to week 12) and a maintenance period (between week 12 and 24). The visit windows are ± 7 days post - randomization. In the table below, there is a detailed summary of the activities.

12.2 STUDY PROCEDURE TABLES

PROCEDURES - SITE VISITS	V1 Scree	V2 Rando	V3	V	V5	V	V7	V	V9	V10	V11 or S24
Study weeks	-	0	S2	S	S6	S	S10	S1	S1	S20	S24
INVESTIGATOR ACTIVITIES											
Obtain the informed consent in writing	X										

Evaluate the inclusion and exclusion criteria	X	X									
Randomization		X									
Blood pregnancy test HCG beta subunit (only in women of childbearing potential)		X	X	X	X	X	X		X	X	
Medical history (with concomitant medication) and physical examination	X										
Blood pressure and pulse	X	X	X	X	X	X	X	X	X	X	X
Electrocardiogram	X										
Complete laboratory test (hemogram; hepatogram; blood glucose; renal function; ionogram; lipids; iron metabolism)	X							X			
Control laboratory test: hemogram			X	X	X	X	X		X	X	
Laboratory measurement of antibodies and hepcidin	X							X			X
Dosing and dose adjustment		X	X	X	X	X	X	X	X	X	
Administration of subcutaneous medication		X	X	X	X	X	X	X	X	X	
Delivery of medication and dosage record card		X	X	X	X	X	X	X	X	X	
Medication control and dose recording			X	X	X	X	X	X	X	X	X
AEs recording		X	X	X	X	X	X	X	X	X	X

12.3 DETAILED STUDY PLAN

12.3.1 Baseline evaluation visit 1 (week -1)

Before performing any study procedure/ evaluation, the patient must have been duly informed on all aspects of the study, including scheduled visits and activities and must sign an informed consent. The patient will be given a signed copy of the informed consent.

The following tasks will be carried out during the baseline visit:

- Review and sign the informed consent with delivery of a signed copy for the patient.
- Evaluate the inclusion and exclusion criteria.
- Samples for full local laboratory test, consisting of:
 - Complete hemogram with reticulocyte (through cytometry or automatic counter) and platelet count.
 - Hepatogram,
 - Glycemia, lipid profile (HDL, LDL and triglycerides)

- Ionogram, calcium, phosphorus, urea and creatinine,
- Serum iron, transferrin, transferrin saturation, and ferritin
- Beta subunit of chorionic gonadotropin only in women of childbearing potential
- Serum sample for antibodies and hepcidin dosage (the sample will be collected and an aliquot will be stored at - 20° C for further analysis)
- Medical history (with concomitant medication) and a physical examination (with weight and height), registering only the clinically relevant findings.
- Pulse: the radial pulse will be measured as an estimate of the heart rate after the patient has rested for 5 minutes.
- Blood pressure: 3 measurements separated by 5 minutes each will be taken, for which the patient should be at rest and sitting. The first measurement will be discarded and the values obtained at the second and third measurements will be averaged, a mean value that will be recorded in the medical history and in the case report form (CRF).
- Electrocardiogram
- The patient will be scheduled for visit 2, which corresponds to randomization.

12.3.2 Randomization visit 2 (week 0)

Visits will be scheduled a week after the baseline screening visit with a window of ± 3 days from the respective date.

The following tasks will be carried out in the consultation during this visit:

- Review the inclusion and exclusion criteria.
- Pulse, will be measured after the patient has rested during 5 minutes.
- Blood pressure: 3 measurements separated by 5 minutes each will be taken, for which the patient should be at rest and sitting. The first measurement will be discarded and the values obtained at the second and third measurements will be averaged, a mean value that will be recorded in the medical history and in the case report form (CRF).
- Patient will be randomized. A randomization number and treatment with HEMAX PFS or EPREX/ ERYPO® will be assigned to each eligible patient.
- Study medication will be dispensed. Patients will receive the study medication (including oral iron supplement) free of charge; in addition, patients will be instructed on the administration of the medication and will be given a card to register dose administration.
- Subcutaneous administration of HEMAX PFS or EPREX/ ERYPO® will be performed.
- The prescribed doses of HEMAX PFS or EPREX/ ERYPO® will be recorded.

- The patient will be scheduled for the next visit, that corresponds to study week 2.

12.3.3 Visit 3, 4, 5, 6, and 7 (weeks 2, 4, 6, 8 and 10 respectively)

Visits will be scheduled two weeks after the prior visit with a window of ± 1 week from the respective date.

The following tasks will be carried out in the consultation in each of these visits:

- Blood pregnancy test (only in women of childbearing potential)
- Pulse, will be measured after the patient has rested for 5 minutes.
- Blood pressure: 3 measurements separated by 5 minutes each will be taken, for which the patient should be at rest and sitting. The first measurement will be discarded and the values obtained at the second and third measurements will be averaged, a mean value that will be recorded in the medical history and in the case report form (CRF).
- Complete hemogram. The result of the local hemoglobin test should be within the same day or before, so as to be able to adjust the study medication dose, if required.
- The study medication will be counted and dispensed, and patients will be given a card to record the application of the doses.
- Subcutaneous administration of HEMAX PFS or EPREX/ ERYPO® will be performed.
- The prescribed doses of HEMAX PFS or EPREX/ ERYPO® will be recorded, controlling the returned empty boxes and the dose recording cards.
- Adverse events will be recorded and will be registered in the medical history and in the CRF.
- The patient will be scheduled for the next study visit.

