9.2 INCLUSION CRITERIA

Patients must meet all of the following inclusion criteria to be eligible for the study:

- 1) Patients between 18 and 85 years of age of both sexes.
- 2) IRC defined by the glomerular filtration rate through the Modification of Diet in Renal Disease Study (MDRD) formula that is ≥ 15 ml/ min and < 60 ml/ min by 1.73 m_2 .
- 3) Anemia with indication of treatment and hemoglobin lower than 10.5 g/ dl and greater

than 7.5 g/ dl.

- 4) Patients who have both the will and the capacity to give informed consent in writing.
- 5) Women with at least 2 years of menopause or surgically sterile 6 months ago or of childbearing potential that have a negative pregnancy test during the baseline visit and are willing to receive an effective birth control method (diaphragm or prophylactic associated with a spermicide since at least 21 days before the first treatment; or intrauterine device in place for at least 3 months before the first dose of epoetin alfa: or hormonal birth control method, in pills, patch or implant, initiated at least 3 months before the first treatment).

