9.3 EXCLUSION CRITERIA

Any of the following criteria exclude the patient from participating in the study:

- 1) Patient with scheduled entry to dialysis or kidney transplant in the next 6 months.
- 2) Transferrin saturation < 20%.
- 3) Cause of renal failure (as the secondary ones to autoimmune diseases) that in the opinion of the physician may affect the normal development of the Protocol.
- 4) Active bleeding or history of hemorrhage that has caused significant decrease of hematocrits in the last 30 days.
- 5) Uncontrolled hypertension (≥ 160 mm Hg systolic pressure and/ or ≥ 100 mm Hg diastolic pressure with anti - hypertensive treatment).
- 6) Anemia due to another cause other than the kidney disease.
- 7) Transfusion in the last 3 months before the baseline or screening visit.
- 8) Treatment with an erythropoiesis stimulating agent in the 3 months prior to the baseline or screening visit.
- 9) Increased risk of thromboembolic disease: Previous history of arterial thromboembolism (CVA, TIA, Acute Coronary Syndrome or other) in the last 6 months or venous thrombosis in the last twelve months prior to the baseline visit; surgery in the last month prior to the baseline visit; prolonged standstill or orthopedic surgery scheduled in the next

6 months or any other factor which in the opinion of the investigator may increase the risk of thromboembolism in the patient.

- 10) Hematological disease, including myelodysplastic syndrome or a history of hematologic neoplasia or solid tumor in the last 5 years.
- 11) History of congestive heart failure.
- 12) Pregnancy or breast - feeding.
- 13) Refusal of patient to participate in the protocol or patients with a medical condition that the investigator considers significantly relevant to prevent their participation in the study.

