10 MEDICATIONS/ TREATMENT AND CONCOMITANT MEDICATIONS

10.1 MEDICATION/ TREATMENT

HEMAX PFS or EPREX/ ERYPO® (both epoetin alfa) at an initial dose of 29 IU/ kg twice a week

subcutaneously (2000 IU twice a week for 70 kg of weight) during the 12 weeks of titration, followed by an equivalent weekly dose during the additional 12 weeks of maintenance.

Usual titration scheme and dose management during the titration phase:

- If the hemoglobin in any visit increases >1 g/ dl in any period of 2 weeks prior to the visit, the dose will be reduced by 25%.
- If the hemoglobin, in any visit, increases to values equal to or greater than 11.5 g/ dl the dose will be interrupted and resumed when the hemoglobin drops below 10.5 g/ dl, with a dose decrease by 25%.

Only every four weeks (weeks 4 and 8) from treatment initiation and during the titration period, the dose may be increased according to the following scheme:

- If after four or eight weeks, hemoglobin does not increase by at least 1 g/ dl as compared to the baseline value, the dose will be increased by 25%.
- If after twelve weeks, hemoglobin did not increase during the titration phase at least 1 g/ dl as compared to the baseline value, the patient will be withdrawn from the study.

Maintenance phase:

Patients who have experienced during the titration phase an increase of the Hb of at least 1 g/ dl as compared to the baseline value, will enter the maintenance phase after week 12 until week 24, with visits every 4 weeks. All patients will be switched to a weekly dosing scheme in which they will receive the same total dose of epoetin alfa administered at the end of the titration phase (for example the patients who at the end of the titration phase are with 2000 IU twice a week will receive 4000 IU weekly during the maintenance phase). During the maintenance phase, the following medication adjustments may be performed:

- If despite receiving the indicated dose of epoetin alfa, the Hb drops below 10.5 g/ dl, the dose may be adjusted by 25%.
- If the hemoglobin, in any visit, increases to values equal to or greater than 11.5 g/ dl, the dose will be interrupted and resumed when the hemoglobin has dropped below 10.5 g/ dl, with a dose decrease by 25%.

[figure not shown]
Application of Medication:

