4.4 Study Variables

	V1 Screen	V2 Random	V3	V4	V5	V6	V7	V8	V9	V10	V11 or Final
PROCEDURES - SITE VISITS											
Study weeks	- 1	0	S2	S4	S6	S8	S10	S12	S16	S20	S24
INVESTIGATOR ACTIVITIES											
Obtain the informed consent in writing	X										
Evaluate the inclusion and exclusion	X	X									
Randomization		X									
Blood pregnancy test HCG beta subunit (only in women of childbearing potential)		X	X	X	X	X	X		X	X	
Medical history (with concomitant medication) and physical examination	X										

Blood pressure and pulse	X	X	X	X	X	X	X	X	X	X	X
Electrocardiogram	X										
Complete laboratory test (hemogram; hepatogram; blood glucose; renal function; ionogram; lipids; iron metabolism)	X							X			
Control laboratory test: hemogram			X	X	X	X	X		X	X	
Laboratory measurement of antibodies and hepcidin	X							X			X
Dosing and dose adjustment		X	X	X	X	X	X	X	X	X	
Administration of subcutaneous		X	X	X	X	X	X	X	X	X	
Delivery of medication and dosage record card		X	X	X	X	X	X	X	X	X	
Medication control and dose recording			X	X	X	X	X	X	X	X	X
AEs recording		X	X	X	X	X	X	X	X	X	X

Randomization Visit 2 (Week 0) will be scheduled a week after the baseline screening visit with a window of ± 3 days from the respective date.

The time-window for randomization visit is one week ± 3 days from screening visit.

The time-window for visits 3, 4, 5, 6, and 7 (weeks 2, 4, 6, 8 and 10) is two weeks ± 1 week. The time-window for visits 9, 10 and 11 (weeks 16, 20 and 24) is four weeks ± 1 week.

Adverse events will be recorded from the moment the patient signed the written informed consent, and they will be recorded all the study long. They will be reviewed and updated in each visit, and anytime the patient will be contacted by telephone

5 Sample Size

A total number of 120 patients (60 in each group) will allow, with 80% of power, to rule out a difference between treatment groups greater than 1g/ dl in hemoglobin increase from baseline value to the mean value of the visits between week 8 and 12.

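### Eligibility is reviewed again at randomisation with no new Hb and with key look-back windows that end at screening, and the week 2 rise rule normally has only a three-week-old Hb to work from (minor)

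*Protocol*

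**What the plan says.** Protocol 12.1 and 12.3.1 treat visit 1 (week -1) as both the screening and the baseline visit, and it has the only hemogram before the first dose. On visit 2, Protocol 12.3.2 states: "Visits will be scheduled a week after the baseline screening visit with a window of ± 3 days from the respective date". SAP 4.4 agrees: "The time-window for randomization visit is one week ± 3 days from screening visit".

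The visit 2 task list opens with "Review the inclusion and exclusion criteria" and then goes through pulse, blood pressure, randomisation and the first dose. It contains no hemogram. In the schedule (Protocol 12.2, repeated in SAP 4.4), the row "Control laboratory test: hemogram" is first marked at visit 3, and the complete laboratory test is marked at visit 1 but not at visit 2.

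The Hb entry criterion in Protocol 9.2 is "Anemia with indication of treatment and hemoglobin lower than 10.5 g/ dl and greater" than 7.5 g/dl. In Protocol 9.3, exclusion 7 reads "Transfusion in the last 3 months before the baseline or screening visit". Exclusion 8 (ESA) uses the same anchor, and the dated parts of exclusion 9 (thromboembolism, surgery) count back from the baseline visit. SAP 4.2 repeats all three. Protocol 8 and 9 give the ESA washout as the last three months, with no anchor visit.

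Protocol 10.1 has a dose rule that is triggered "If the hemoglobin in any visit increases >1 g/ dl in any period of 2 weeks prior to the visit". Protocol 14.2.8 lists the hemogram visits starting at week 4, whereas 12.2 and 12.3.3 require one at week 2.

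**The concern.** An eligibility review just before randomisation should confirm that the patient still qualifies. Here the Hb limits cannot be confirmed again from scheduled data. The transfusion, ESA, thromboembolism and surgery windows, read literally, stop at visit 1 and leave 4 to 10 days uncovered. Followed as written, the criteria could admit a patient whose washout was broken after baseline Hb was drawn.

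The single qualifying value also carries weight later. It is the reference for the primary change score, the responder rate, the within-arm analyses, the week 4 and week 8 dose decisions, and withdrawal or entry to maintenance at week 12. A reading selected for being below 10.5 g/dl is on average lower than the patient's true level, so some later rise is expected without any drug effect. There is no untreated arm to show how much.

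Finally, the rise rule at week 2 needs an Hb from about two weeks earlier. An on-time week 2 visit puts that point at visit 2, where none is taken.

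**Working it through.** **Visit intervals.** Inputs: visit 2 at 7 ± 3 days after visit 1 (Protocol 12.3.2, SAP 4.4); visit 3 at 14 ± 7 days after visit 2 (Protocol 12.3.3).

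- Visit 1 to visit 2: 7 − 3 = 4 to 7 + 3 = 10 days.
- Visit 1 Hb to week 2 Hb, as scheduled: 7 + 14 = 21 days.
- With week 2 on time: 4 + 14 = 18 to 10 + 14 = 24 days.
- Over all windows: 4 + 7 = 11 to 10 + 21 = 31 days.
- Whole-day combinations: 7 × 15 = 105. Those totalling 14 days or less: 4 + 3 + 2 + 1 = 10, or 9.5%. All of them need a week 2 visit 7 to 10 days after randomisation. This counts window days and does not estimate how often it happens.
- A 1 g/dl rise over 21 days averages 14/21 = 0.67 g/dl per 14 days. Over 31 days it is 14/31 = 0.45, and over 11 days 14/11 = 1.27. The visit 1 value therefore does not show whether a two-week rise passed 1 g/dl.

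**Look-back windows side by side.**

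| Criterion | Anchor in Protocol 9.3 | Event between visits 1 and 2 |
|---|---|---|
| 4, bleeding (30 days) | none stated | can be read as covered |
| 7, transfusion | baseline or screening visit | not a breach as worded |
| 8, ESA | baseline or screening visit | not a breach as worded, but in conflict with Protocol 8 and 9 |
| 9, thromboembolism and surgery (dated parts) | baseline visit | not a breach of the dated parts |
| 10, tumour (5 years) | none stated | can be read as covered |

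**Size of the selection effect.** Neither document gives an SD for Hb, so these are assumptions: true Hb in the screened population with SD 0.9 and mean 9.5 to 10.5 g/dl; within-patient SD 0.3 to 0.5. Each reading is the true value plus independent error, and patients are kept if the first reading lies between 7.5 and 10.5. I simulated 2 million patients per setting, with no treatment effect.

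| Setting | Mean rise from visit 1 | Visit 2 reading ≥ 10.5 | Rise > 1 g/dl from visit 1 value | Rise > 1 g/dl from a fresh visit 2 value |
|---|---|---|---|---|
| mean 9.5, within SD 0.3 | 0.02 g/dl | 4.9% | 1.0% | 0.9% |
| mean 10.5, within SD 0.5 | 0.19 g/dl | 22.4% | 11.7% | 7.9% |

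The last two columns compare single readings. Their difference is the part due to selection: about 1.0 − 0.9 = 0.1 to 11.7 − 7.9 = 3.8 percentage points. The rest is ordinary variation between two readings.

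With the mean of visits 1 and 2 as baseline, the shift falls to 0.01 to 0.10 g/dl. With visit 2 alone it is about 0.

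Under wider assumptions (population mean 10 to 11, between-patient SD 1.0 to 1.3, within-patient SD 0.3 to 0.7) the shift is 0.03 to 0.43 g/dl. At the top of that range, 27% show a rise above 1 g/dl from the visit 1 value against 16% from a fresh one, a gap of 11 points.

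**The case against.** A one-week-old screening value is a defensible baseline, nothing forbids a repeat Hb, and the visit 2 review is not empty: blood pressure is re-measured and the schedule marks a pregnancy test. All of that stands. Four stronger readings are tempting, and the documents do not support them.

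- *The equivalence comparison is biased.* It is not, in expectation. Baseline precedes randomisation, so both arms share the shift, and the ANCOVA in Protocol 16.5 adjusts for baseline. The t test that SAP 7 and 8 allow as an alternative does not adjust for chance baseline imbalance, which matters more with 23 and 20 patients.
- *Every look-back ends at screening.* Bleeding and tumour history have no anchor, and Protocol 8 and 9 leave the ESA washout unanchored. Investigator judgement under exclusions 9 and 13 may also catch a TIA or surgery between visits. It is discretionary, however, and no rule requires it.
- *A transfusion between the visits would be credited to the study drug.* This is partly handled: Protocol 11.3 withdraws transfused patients, and Protocol 14.1 defines response as a rise without transfusion. Neither states whether it covers the days before randomisation.
- *The week 2 rule has no starting value.* It has one, normally too old. The mismatch is also not confined to week 2: with windows of ± 1 week, successive hemograms can be 7 to 21 days apart, and a visit 2 hemogram would leave that same range at week 2.

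**Conclusion.** The point holds as a minor one. The missing visit 2 hemogram, the 4 to 10 uncovered days in exclusions 7, 8 and 9, and the 21-day (11 to 31) age of the only Hb before week 2 all follow from the text and need no assumption. Two internal conflicts also need resolving: the ESA washout (Protocol 8 and 9 against 9.3) and the week 2 hemogram (14.2.8 against 12.2 and 12.3.3).

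The exposed results are the within-arm change and the +1 g/dl responder rate. The 0.02 to 0.19 g/dl shift rests wholly on assumed SDs and an assumed population mean. Most chance rises above 1 g/dl in that simulation are measurement noise and would occur with a fresh baseline too. A reader might infer that the primary equivalence result is compromised; the design does not support that. The documents also do not show whether any patient had an event between visits 1 and 2.

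**What to change.** For the protocol text, or a successor, since SAP 5 reports that recruitment has ended:

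- Anchor exclusions 7, 8 and 9 to randomisation (visit 2), and align Protocol 8 and 9 with them. This is a wording change only.
- Add a pre-dose hemogram at visit 2 (Protocol 12.2 and 12.3.2, SAP 4.4) and state which Hb is baseline. Visit 2 alone removes the selection shift; the mean of visits 1 and 2 only halves it but is more precise. The cost is one routine blood test at an existing visit, and a stated rule for patients whose two values fall on either side of 10.5 g/dl.
- Reconcile the two-week rise rule (Protocol 10.1) with the Hb values the schedule supplies (12.2, 12.3.3, 14.2.8). No dose rule is proposed here.

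For the 43 patients already enrolled:

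- List any transfusion, ESA dose, surgery or thromboembolic event between visits 1 and 2 as an eligibility deviation. Say whether each case leaves the per-protocol set, because SAP 7.2 allows exclusion for unmet eligibility.
- State in the SAP that the visit 1 Hb is baseline, and use the baseline-adjusted ANCOVA, not the t test.
- Caveat the within-arm and responder results for regression to the mean.

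These last steps cost a data listing and a few sentences.
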